---

**Study Physician Name and Contact Information will be provided separately**

## PROTOCOL AMENDMENT SUMMARY OF CHANGES TABLE

DOCUMENT HISTORY	
Document	Date
Amendment 2 (Version 3.0)	04 September 2020
Amendment 1 (Version 2.0)	25 June 2020
Original Protocol (Version 1.0)	20 May 2020

### **Amendment 2 (04 September 2020)**

The overall rationale for the amendment was to provide clarification regarding laboratory tests for HBV and HCV during screening.

COVID-19 pneumonia requiring hospitalization is an acute disease that requires a rapid screening evaluation to ensure prompt initiation of study treatment. The Sponsor is aware that at some institutions, the turnaround times for local hepatitis virus tests are prolonged (days rather than hours), leading to substantial delays in treatment initiation. Thus, the Sponsor has reviewed the risks and benefits of initiating treatment before these test results are available. In the acute setting of severe COVID-19 disease, the potential benefits of initiating treatment in a timely manner outweigh potential risks, especially considering that 1) HBV/HCV events are expected to be infrequent based on Sponsor data from oncology studies, 2) the short duration of therapy is anticipated to further reduce risk, and 3) HBV/HCV events can be monitored and, if necessary, managed with antiviral therapies.

No reports of HCV reactivation have been received in the acalabrutinib clinical program to date, and there are no published reports of HCV reactivation following treatment with BTK inhibitors that are available to the Sponsor. Hepatitis B virus reactivations in the setting of acalabrutinib treatment are infrequently reported. Among 4053 participants across all clinical studies investigating acalabrutinib to date, 9 participants had reactivations (1 fatal, 8 non-serious) after a median duration of therapy of 248 days (range 43 to 582 days). Hepatitis B virus reactivations have rarely been reported with other BTK inhibitors, such as ibrutinib, where a larger number of patients have been treated to date in clinical studies and real-world settings; ibrutinib has been approved for use since 2014 (Hammond et al 2018). Furthermore, when HBV reactivations occur, they are typically observed following months to years of treatment and are easily managed with antiviral therapy with good outcomes; in many cases, the BTK inhibitor is continued.

Section Number and Name	Description of Change	Brief Rationale	Substantial/ Non-substantial
1.3 Schedule of Activities (Table 1)	Removed Day 1 column from Table 1. Made changes to “Daily until hospital discharge” column to adjust for this change.	Clarification	Non-substantial
1.3 Schedule of Activities (Table 1), 5.1 Inclusion Criteria	Revised SARS-CoV-2 PCR virus testing Inclusion Criterion 3 in Section 5.1 and aligned the SoA (Table 1) accordingly.	To allow flexibility	Non-substantial
1.3 Schedule of Activities (Table 1), 8.2.5.1 Local Laboratory Tests, 8.2.5.1.1 Hepatitis Serology Guidelines	Added text to footnote d of Table 1 to indicate that treatment with acalabrutinib can start after blood samples for all HBV and HCV serology tests and for both HBV and HCV PCR tests have been collected, even if the results are not available at the time of the first dose. In addition, added hepatitis serology guidelines that should be followed (Section 8.2.5.1.1).	See rationale provided above this table	Substantial
1.3 Schedule of Activities (Table 1), 8.2.5.2 Central Laboratory Tests	In Table 1, specified that a nasopharyngeal swab will be collected for SARS-CoV-2 viral load/viral shedding. In Section 8.2.5.2, changed [REDACTED]	To correct typographical error	Non-substantial
2.3.1.3 Hepatitis B and C Reactivation	Added information about HCV and HBV reactivation with acalabrutinib	To support hepatitis serology guidelines	Substantial
5.1 Inclusion Criteria	Revised Inclusion Criterion 5 to indicate that feeding tube must remain in place for a minimum of 3 days after study enrollment	Clarification	Non-substantial
5.2 Exclusion Criteria	Revised Exclusion Criterion 9 to align with the hepatitis serology guidelines	Clarification and consistency	Substantial
	Added an exception to Exclusion Criterion 12 to indicate that AST and/or ALT can be up to 5 × ULN if considered due to underlying COVID-19, but cannot be associated with concurrent elevated bilirubin (up to 2 × ULN)	Hepatotoxicity and ALT/AST are not currently adverse drug reactions for acalabrutinib and there is evidence for ALT/AST increases	Substantial

Section Number and Name	Description of Change	Brief Rationale	Substantial/ Non-substantial
	
Revised Exclusion Criterion 19 to clarify that aspirin and therapeutic/ high doses of low-molecular-weight heparin are not allowed, but that aspirin and prophylactic/low doses of low-molecular-weight heparin are allowed
	
associated with COVID-19 (Cai et al 2020, Guan et al 2020a)
 
Clarification
	
Non-substantial


7.1 Discontinuation of Study Intervention, 7.2 Participant Withdrawal from the Study
	
Added that participants with positive HBsAg, HBV-DNA, or HCV-RNA test result after first dose administration will be discontinued from study intervention (Section 7.1) and withdrawn from the study (Section 7.2)
	
To align with hepatitis serology guidelines
	
Substantial

Clinical Study Protocol Signature Page
	
Removed
	
Utilizing different signoff process
	
Non-substantial

ALT = alanine aminotransferase; AST = aspartate aminotransferase; COVID-19 = coronavirus disease 2019; HBsAg = hepatitis B surface antigen; HBV = hepatitis B virus; HCV = hepatitis C virus; PCR = polymerase chain reaction; SARS-CoV-2 = severe acute respiratory syndrome coronavirus 2; SoA = Schedule of Activities; ULN = upper limit of normal.

# 1 PROTOCOL SUMMARY

## 1.1 Synopsis

### Protocol Title

An Open-label, Multiple-dose Study to Evaluate the Pharmacokinetics, and Safety and Tolerability of Acalabrutinib Suspension Delivered via Nasogastric Tube, Coadministered With a Proton-pump Inhibitor, in Participants Hospitalized With COVID-19

### Short Title

Study of Acalabrutinib Suspension Delivered via Nasogastric Tube With a Proton-pump Inhibitor in Hospitalized COVID-19 Participants

### Rationale

This study is being conducted to support the ongoing clinical development of acalabrutinib (CALQUENCE®) in hospitalized COVID-19 patients. Because many COVID-19 patients may be unable to swallow capsules due to respiratory failure (eg, they may require endotracheal intubation for ventilator support and NG tube placement), it is important to have a clinically acceptable method to administer acalabrutinib (capsules) via NG tube. Furthermore, due to the acute illness of COVID-19 patients, many hospitalized patients are placed on high doses of PPIs or continuous H2-receptor antagonists to prevent stress ulcers. This study is designed to determine the PK, and safety and tolerability of acalabrutinib suspension, when coadministered with a PPI, in participants with confirmed SARS-CoV-2 infection requiring hospitalization due to respiratory failure (as defined in the table below) attributable to COVID-19 pneumonia and who have an NG tube in place.

### Objectives and Endpoints

Objective	Endpoint/Variable
Primary Objectives	Primary Endpoints/Variables

To characterize the PK of acalabrutinib and its active metabolite (ACP-5862) following administration of acalabrutinib suspension, when coadministered with a PPI, in participants with COVID-19

	

Primary PK parameters for acalabrutinib and ACP-5862 include AUC12h, AUClast, and Cmax. Additional PK parameters are described in the protocol.

To assess the safety and tolerability of acalabrutinib suspension in participants with COVID-19 when administered in the presence of PPIs and BSC

	

Type, frequency, severity, and relationship to study intervention of any treatment-emergent AEs or abnormalities of laboratory tests, SAEs, or AEs leading to discontinuation of study intervention

 CALQUENCE® is a trademark of the AstraZeneca group of companies.

Objective	Endpoint/Variable
Secondary Objective	Secondary Endpoints/Variables

 
To evaluate the preliminary efficacy of adding acalabrutinib suspension to BSC for treatment of participants with COVID-19
 
	
 
Proportion of participants alive and free of respiratory failure at Days 14 and 28  For the purpose of this study, respiratory failure is defined based on resource utilization of any of the following modalities: 
 
Endotracheal intubation and mechanical ventilation
 
Oxygen delivered by high-flow nasal cannula (heated, humidified, oxygen delivered via reinforced nasal cannula at flow rates > 20 L/min with fraction of delivered oxygen <math>\geq 0.5</math>)
 
Noninvasive positive pressure ventilation or continuous positive airway pressure
 
Extracorporeal membrane oxygenation
 
 
 
Percent change from baseline in CRP (time frame: baseline, Days 3, 5, 7, 14, 28)
 
Time to improvement defined as time to clinical improvement of <math>\geq 2</math> points (from first dose date) on a 9-point category ordinal scale, live discharge from the hospital, or considered fit for discharge (a score of 1 or 2 on the ordinal scale), whichever comes first, by Day 28
 

Exploratory Objectives	Exploratory Endpoints/Variables

### Overall Design

This is an open-label, multi-dose study to evaluate the PK, and safety and tolerability of acalabrutinib suspension, when coadministered with a PPI, in participants with confirmed SARS-CoV-2 infection requiring hospitalization due to respiratory failure (as defined in the table above) attributable to COVID-19 pneumonia and who have an NG tube in place. Approximately 20 participants will be included to ensure at least 16 participants are evaluable. Participants are considered evaluable if they have an evaluable PK profile, ie: (1) complete PK Visit 2 assessments; (2) receive active treatment; and (3) do not have unavailable or

incomplete data that may influence the PK analysis.

In addition to receiving BSC, participants will receive acalabrutinib suspension (ie, acalabrutinib 100 mg suspension in COCA-COLA® delivered via NG tube) bid for 14 days (a maximum of 28 doses). Best supportive care is per discretion of the Investigator and institutional guidelines. Standard NG tubes supplied by the hospital will be used. Nasogastric tube placement in the stomach will be confirmed by chest x-ray.

To assess the effect of PPIs, all participants must be receiving treatment with a PPI at the start of the study. Treatment with a PPI can begin at any time prior to enrollment, provided participants have received PPI treatment for at least 24 hours prior to the first dose of acalabrutinib suspension. Any PPI is permitted, provided it meets the minimum equivalent daily dose of 20 mg rabeprazole. Participants must be on this dosage of PPI at the start of the study. They may be weaned off PPIs during the study if medically appropriate.

Blood samples for plasma PK assessment of acalabrutinib and its metabolite (ACP-5862) will be collected at pre-dose and 0.5, 1, 2, 4, 6, and 12 hours following treatment with acalabrutinib suspension as described in the table below. Note that the sample at 12 hours must be collected prior to the subsequent acalabrutinib dose (for trough PK sample).

PK Visit	Description	Rationale
PK Visit 1	First PK sampling will occur on Day 1 (ie, first dosing day for acalabrutinib suspension)	Allows an early assessment of acalabrutinib and ACP-5862 PK in participants receiving acalabrutinib suspension via NG tube
PK Visit 2	Second PK sampling will occur a minimum of 4 days after the start of PPI treatment, irrespective of the timing of NG tube placement and any time after 2 doses of acalabrutinib suspension have been given (ie, PK sampling can begin prior to the third dose, or anytime thereafter)  PK Visit 2 can occur as early as Day 2 (if participant has been on a PPI for $\geq 4$ consecutive days prior to receiving the third acalabrutinib dose), and up to Day 4 (if participant initiated PPI treatment 24 hours prior to receiving the first dose of acalabrutinib on Day 1)	PPI exposure must occur for 4 consecutive days to reach the maximum PPI on-target effect PK sample can commence at any point after the second dose of acalabrutinib suspension to ensure steady-state levels of the active metabolite and maximal [REDACTED] has been reached
PK Visit 3	Third PK sampling will occur 3 days after PK Visit 2, OR on the last day the participant receives acalabrutinib treatment, whichever comes first	Allows an additional opportunity to assess the steady-state PK of acalabrutinib and ACP-5862 PK following delivery of acalabrutinib suspension via NG tube

Safety assessments, including AE reporting, will be performed through 28 ( $\pm 3$ ) days after the last dose of the acalabrutinib suspension.

## Disclosure Statement

This is a single-arm, treatment study that is not blinded.

## Number of Participants

Approximately 20 participants will be enrolled to have at least 16 evaluable participants.

**Note:** “Enrolled” means a participant’s, or his/her legally acceptable representative’s, agreement to participate in a clinical study following completion of the informed consent process. Potential participants who are screened for the purpose of determining eligibility for the study but are not randomly assigned/assigned in the study, are considered “screen failures”, unless otherwise specified by the protocol.

## Intervention Groups and Duration

Treatment with acalabrutinib suspension (ie, acalabrutinib 100 mg suspension in COCA-COLA delivered via NG tube) will be initiated on Day 1. All participants must have received PPI treatment for at least 24 hours prior to the first dose of acalabrutinib suspension. All participants will receive acalabrutinib suspension bid, approximately 12 hours apart, for 14 days (a maximum of 28 doses). The acalabrutinib suspension must be prepared according to the Handling Instructions.

## Safety Review Committee

An SRC will be established to conduct scheduled reviews of safety and other relevant data, enable early identification of safety signals in the study, and minimize the risk to participants during the study, in accordance with the SRC charter (see Section 9.6 for details).

## Statistical Methods

### Pharmacokinetics

A listing of PK blood sample collection times as well as derived sampling time deviations will be provided. Plasma acalabrutinib and ACP-5862 concentrations and PK parameters listed below will be summarized using appropriate descriptive statistics.

- Primary PK parameters:  $AUC_{12h}$ ,  $AUC_{last}$ , and  $C_{max}$ .
- Secondary PK parameters:  $t_{1/2}$ ,  $t_{max}$ , and  $\lambda_z$  (acalabrutinib and ACP-5862);  $CL/F$  and  $V_z/F$  (acalabrutinib); and  $C_{max}$ ,  $AUC_{last}$ , and  $AUC_{12h}$  (metabolite to parent ratio).

### Safety

Safety assessments will consist of monitoring and recording of AEs, SAEs, and AEs leading to discontinuation of study intervention; measurement of protocol-specified vital signs, ECG, laboratory variables and other protocol-specified safety tests or measurements. All safety

analyses will be performed on the Safety Analysis Set. Verbatim descriptions of AEs will be mapped according to the latest version of MedDRA and graded according to NCI CTCAE v5.0 or higher. Treatment-emergent AEs will be summarized, unless otherwise specified. Treatment-emergent AEs are defined as AEs starting or ongoing AEs worsening after the first dose of study intervention and AEs with start date up to the last dose of study intervention plus 28 ( $\pm$  3) days.

[figure not shown]
### Efficacy

All efficacy analyses will be performed on the Efficacy Evaluable Set. For the proportion of participants alive and free of respiratory failure at Days 14 and 28, point estimates and their 90% confidence intervals will be calculated. Summary statistics (n, mean, median, standard deviation, minimum, and maximum) will be presented for the percent change from baseline in CRP at the specified time points. Time to improvement defined as time to clinical improvement of at least 2 points (from first dose date) on a 9-point category ordinal scale, live discharge from the hospital, or considered fit for discharge (a score of 1 or 2 on the ordinal scale), whichever comes first, by Day 28 (this will also define the “responder” for the response rate analyses), will be analyzed using the Kaplan-Meier method.

## **1.2 Schema**

The study design is illustrated in Figure 1.

**Figure 1 Study Design**

Scenarios of PK visits relative to PPI start	PPI Dosing Starts (≥24 h prior to first acalabrutinib dose)	PK Visit 1 a (coincides with Day 1 of study)	PK Visit 2 a (≥4 d after start of PPI and any time after 2 doses of acalabrutinib)	PK Visit 3 a (3 days after PK Visit 2 or on last day of acalabrutinib treatment)
Scenario 1 (shown in figure)	Day -1	Prior to first acalabrutinib dose	Day 3 (prior to fifth dose)	Day 6 (prior to 11th dose)
Scenario 2	Day -2	Prior to first acalabrutinib dose	Day 2 (prior to third dose)	Day 5 (prior to ninth dose)
Scenario 3	Day -3	Prior to first acalabrutinib dose	Day 2 (prior to third dose)	Day 5 (prior to ninth dose)
Scenario 4	Day -4 or earlier	Prior to first acalabrutinib dose	Day 2 (prior to third dose)	Day 5 (prior to ninth dose)

a Blood samples for plasma PK assessment of acalabrutinib and its metabolite (ACP-5862) will be collected at pre-dose and 0.5, 1, 2, 4, 6, and 12 hours following treatment with acalabrutinib suspension. Note that the sample at 12 hours must be collected prior to the subsequent acalabrutinib dose (for trough PK sample).

Note: PK Visit 2 can occur as early as Day 2 (if participant has been on a PPI for ≥ 4 consecutive days prior to receiving the third acalabrutinib dose), and up to Day 4 (if participant initiated PPI treatment 24 hours prior to receiving the first dose of acalabrutinib on Day 1). See Table 4 for more information.

bid = twice daily; PK = pharmacokinetic(s); PPI = proton-pump inhibitor.

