- f If a participant is discharged prior to Day 14, he/she needs to visit the site for an assessment 2 to 4 days after discharge. Assessments should match those for Day 14.
- g All participants should have follow-up assessments for safety 28 (± 3) days after the last dose of acalabrutinib.
- h Telemedicine is recommended for capturing adverse events, concomitant medications, and survival status. Safety laboratory tests can be done at the hospital or a local laboratory provided the results are ultimately captured in the clinical database for the study.
- i **PK Visit 1:** PK sampling will occur on Day 1 (ie, first dosing day for acalabrutinib suspension).  
**PK Visit 2:** PK sampling can occur as early as Day 2 (if participant has been on a PPI for ≥ 4 consecutive days prior to receiving the third acalabrutinib dose), and up to Day 4 (if participant initiated PPI treatment 24 hours prior to receiving the first dose of acalabrutinib on Day 1). See Section 4.1 for additional details.  
**PK Visit 3:** PK sampling will occur 3 days after PK Visit 2, OR on the last day the participant receives acalabrutinib treatment, whichever comes first.
- j PK sampling will occur at pre-dose and 0.5 (± 5 min), 1 (± 5 min), 2 (± 15 min), 4 (± 15 min), 6 (± 15 min), and 12 (± 60 min) hours post-dose, [REDACTED] sampling will occur at pre-dose and 4 (± 15 min) and 12 (± 60 min) hours post-dose. The 12-hour post-dose PK [REDACTED] samples will be collected immediately prior to administration of the subsequent acalabrutinib dose.
- k The timing of PK [REDACTED] sample collections should be aligned as closely as possible and will be prioritized over other blood samples being collected simultaneously, except in the case of an adverse event for which relevant assessment/blood sample collection will be prioritized.
- l [REDACTED]
- m [REDACTED]
- n Screening can be performed within 1 to 3 days prior to dosing, depending on the local requirements for laboratory turnaround times; ECG can be collected at any time during this screening window.
- o Fibrinogen, PT, aPTT, INR, D-dimer, and cardiac troponin I should be performed more frequently if clinically indicated.

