**Table 4 Pharmacokinetic Sampling Relative to Start of Proton-pump Inhibitor Treatment**

PK Visit	Description	Rationale
PK Visit 1	First PK sampling will occur on Day 1 (ie, first dosing day for acalabrutinib suspension)	Allows an early assessment of acalabrutinib and ACP-5862 PK in participants receiving acalabrutinib suspension via NG tube
PK Visit 2	Second PK sampling will occur a minimum of 4 days after the start of PPI treatment, irrespective of the timing of NG tube placement and any time after 2 doses of acalabrutinib suspension have been given (ie, PK sampling can begin prior to the third dose, or anytime thereafter) PK Visit 2 can occur as early as Day 2 (if participant has been on a PPI for $\geq 4$ consecutive days prior to receiving the third acalabrutinib dose), and up to Day 4 (if participant initiated PPI treatment 24 hours prior to receiving the first dose of acalabrutinib on Day 1)	PPI exposure must occur for 4 consecutive days to reach the maximum PPI on-target effect PK sample can commence at any point after the second dose of acalabrutinib suspension to ensure steady-state levels of the active metabolite and maximal [REDACTED] [REDACTED] [REDACTED] has been reached
PK Visit 3	Third PK sampling will occur 3 days after PK Visit 2, OR on the last day the participant receives acalabrutinib treatment, whichever comes first	Allows an additional opportunity to assess the steady state PK of acalabrutinib and ACP-5862 PK following delivery of acalabrutinib suspension via NG tube

[REDACTED] NG = nasogastric; PK = pharmacokinetic(s); PPI = proton-pump inhibitor.

Safety assessments, including AE reporting, will be performed through 28 ( $\pm 3$ ) days after the last dose of the acalabrutinib suspension.

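### Figure 1 places PK Visit 2 at a nominal 72 hours of PPI in Scenarios 1 and 2, which conflicts with the 4-day minimum in its own column header, in Table 4 and in the Day 4 note

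*Protocol*

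**What the plan says.** **The rule.** Table 4 (Section 4.1) states: "Second PK sampling will occur a minimum of 4 days after the start of PPI treatment". Its reason is: "PPI exposure must occur for 4 consecutive days to reach the maximum PPI on-target effect". The synopsis table repeats the rule, and the PK Visit 2 column of Figure 1 carries it in its header: "≥4 d after start of PPI".

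**The two worked cases.** The note under Figure 1, Table 4 and footnote i of the Schedule of Activities give the same two cases:
- Day 2 is allowed "if participant has been on a PPI for ≥ 4 consecutive days prior to receiving the third acalabrutinib dose".
- The visit may fall "up to Day 4 (if participant initiated PPI treatment 24 hours prior to receiving the first dose of acalabrutinib on Day 1").

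**The printed schedule.** Figure 1 lists four scenarios by the day the PPI was started:
- Scenario 1 (Day -1): PK Visit 2 on "Day 3 (prior to fifth dose"), PK Visit 3 on Day 6 before dose 11.
- Scenario 2 (Day -2): PK Visit 2 on "Day 2 (prior to third dose"), PK Visit 3 on Day 5 before dose 9.
- Scenarios 3 and 4 (Day -3; Day -4 or earlier): the same visit days as Scenario 2.

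**Day numbering.** The screening column of the Schedule of Activities is labelled Day -3 to Day -1. Footnote n explains it: "Screening can be performed within 1 to 3 days prior to dosing". No Day 0 appears anywhere in the protocol.

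**The concern.** Two cells of Figure 1 do not meet the condition printed at the head of their own column. Scenario 1 also differs from the note directly beneath it: a PPI start one day before dosing gives Day 3 in the table and Day 4 in the note.

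The visit matters. Section 4.1 makes completion of PK Visit 2 part of the definition of an evaluable participant, and Section 9.2 sizes the study to obtain 16 such participants. PK is a primary objective, and PK Visit 2 is the profile meant to follow 4 consecutive days of PPI. A site that schedules from Figure 1 would sample recent PPI starters about a day before a site that schedules from Table 4, and both profiles would carry the same visit label. Section 2.2.3.4 says that raised gastric pH lowers acalabrutinib exposure. If acid suppression is still building, an early profile could therefore make the suspension look better than it would at full PPI effect.

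**Working it through.** **Inputs**
- Dosing every 12 hours (Section 6.1.2.1), so dose k falls 12 × (k − 1) hours after dose 1.
- Day -1, -2, -3 and -4 are 1, 2, 3 and 4 days before Day 1 (footnote n; no Day 0).
- Matched clock times: the PPI is started at the same hour of day as dose 1. This is an assumption, as the protocol gives no PPI clock times.
- Minimum PPI exposure: 4 days = 96 hours.

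**Formula.** PPI hours at the pre-dose sample = 24 × (days of PPI before Day 1) + 12 × (dose number − 1).

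**The note first.** PPI started 24 hours before dose 1, visit on Day 4 before dose 7: 24 + 72 = 96 hours. The note reproduces the 4-day rule exactly, so it counts elapsed days.

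**Figure 1, PK Visit 2**

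| Scenario | PPI start | Printed visit | PPI hours | Against 96 h |
|---|---|---|---|---|
| 1 | Day -1 | Day 3, dose 5 | 24 + 48 = 72 | 24 short |
| 2 | Day -2 | Day 2, dose 3 | 48 + 24 = 72 | 24 short |
| 3 | Day -3 | Day 2, dose 3 | 72 + 24 = 96 | met |
| 4 | Day -4 or earlier | Day 2, dose 3 | at least 96 + 24 = 120 | met |

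In Scenarios 1 and 2 the last sample of the profile, 12 hours after the dose, falls at 72 + 12 = 84 hours, still under 96.

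**Without matched clock times.** In Scenario 1 the PPI start is at least 24 and under 48 hours before dose 1, giving 72 to just under 96 hours. In Scenario 2 the start can be anywhere on Day -2, giving 48 to just under 96 hours. Neither reaches 96 hours before the dose, because Day -1 to Day 3 and Day -2 to Day 2 each span only four calendar days from first minute to last. Scenario 3 then ranges from 72 to just under 120 hours, so its compliance is also nominal.

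**Earliest times that satisfy the stated rule**
- Scenario 1: dose 7 on Day 4 (24 + 72 = 96).
- Scenario 2: dose 5 on Day 3 (48 + 48 = 96).

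**PK Visit 3 as printed**
- Scenario 1: 24 + 120 = 144 hours.
- Scenario 2: 48 + 96 = 144 hours.

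**The case against.** **A Day 0 might be intended.** If the figure counted one, Scenario 1 would be 48 + 48 = 96 hours and Scenario 2 would be 72 + 24 = 96 hours, and the Day 4 note would still fit. This is the best defence, and the timeline drawing that might settle it was not available for this check. The text is against it. The Schedule of Activities equates Day -3 to Day -1 with 1 to 3 days before dosing. A Day 0 would also leave the minimum permitted PPI start, 24 hours before dosing, without a scenario. If a Day 0 is meant, the protocol has to say so.

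**Inclusive counting.** Counting Days -1, 1, 2, 3 or Days -2, -1, 1, 2 puts the visit on the fourth PPI day, which suits the wording of the rationale. It does not suit a minimum of 4 days after the start, and it would turn the note's Day 4 into Day 3.

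**Day 4 as an outer limit only.** Even so, the 4-day minimum excludes Day 3 in Scenario 1.

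**Table 4 governs.** Section 8.5.1 says PK samples are collected as Table 4 describes, and Figure 1 refers the reader to it. This stands: a careful site could comply. But the figure gives the concrete visit days, and two of them are wrong under the rule.

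**The impact is limited.** This also stands in part. PK Visit 3 is scheduled at a nominal 144 hours. The PK Analysis Set (Table 9) does not depend on PPI hours, PK Visit 2 already allows varying PPI durations above the minimum, and no formal PK test is planned (Section 9.4.2). PK Visit 3 is not a full substitute, since evaluability does not rest on it, PPIs may be weaned during the study, and the tube need only be expected to stay in place for 3 days after enrollment.

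**Conclusion.** The inconsistency is real. Under the protocol's own day numbering and matched clock times, Figure 1 places PK Visit 2 at 72 hours of PPI in two of its four scenarios, 24 hours below the minimum in its header and in Table 4, and Scenario 1 disagrees with the Day 4 note. The shortfall in Scenarios 1 and 2 does not depend on the clock-time assumption; the exact figure of 72 does.

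A reader might go further and infer that the 42% reduction in AUC and 73% reduction in Cmax in Section 2.2.3.4 measure the bias at stake. They do not. Those figures compare acalabrutinib after omeprazole with normal acidic conditions, which is the whole PPI interaction and not the difference between 72 and 96 hours. The documents give no basis for sizing that difference. Nor do they support treating every early profile as unusable: the stated consequence is a mixture of PPI durations under one label, partly offset by PK Visit 3.

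**What to change.** - Reconcile Scenarios 1 and 2 in Figure 1 with the column header, the note and Table 4. If the 4-day rule stands as written, the earliest matching PK Visit 2 times are Day 4 before dose 7 (Scenario 1) and Day 3 before dose 5 (Scenario 2). PK Visit 3, three days later, would move to Day 7 before dose 13 and Day 6 before dose 11.
- State the day-numbering convention, including whether there is a Day 0.
- Express the PK Visit 2 rule in hours from the start of the PPI. This also settles borderline cases in Scenario 3.
- Record the PPI start time. Section 6.5 already requires start and end dates for concomitant medication but does not ask for clock time.
- Flag PK Visit 2 profiles taken before the minimum and give a sensitivity summary without them. Automatic exclusion from the main summary could cost evaluable participants from a target of 16.

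These changes concern sampling times and records only. The cost is one corrected table, a site memo and one extra data field. For recent PPI starters, PK Visits 2 and 3 would fall one day later than Figure 1 now shows, with a slightly higher chance of losing a profile.
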